### *3.6.2 Clinical Laboratory Tests*

All standard blood tests will be analyzed by the local laboratory as specified in the Schedule of Procedures (Appendix A). A list of laboratory tests to be performed is included in Appendix B.

The incidence of abnormalities (as defined by normal ranges) after the first dose of study drug will be summarized with counts and percentages of subjects for each treatment group.

Post-baseline clinically significant lab results will also be summarized with counts and percentages of subjects for each treatment group.

All abnormal lab data will be listed.

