7 ENDPOINTS

7.1 Primary Endpoint

The primary endpoint is the safety of ADX-629, determined by evaluation of the following:

- AEs;
- Safety laboratory tests (including chemistry, hematology, coagulation parameters, and urinalysis);
- Vital signs (including heart rate, blood pressure, respiratory rate, temperature, and oxygen saturation);
- Physical examinations; and
- 12-lead ECGs.

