Clinically significant abnormal laboratory or other examination (e.g., ECG) findings that are detected during the clinical trial or are present at Screening and significantly worsen during the clinical trial should be reported as AEs, as described below. The Investigator will exercise his or her medical and scientific judgment in deciding whether an abnormal laboratory finding or other abnormal assessment is clinically significant. Clinically significant abnormal laboratory values occurring during the clinical trial will be followed until repeat tests return to normal, stabilize, or are no longer clinically significant. Abnormal test results that are determined to be an error should not be reported as an AE. Laboratory test results that are abnormal, but not clinically significant

as determined by the Investigator, should not be reported as an AE. Laboratory abnormalities or other abnormal clinical findings (e.g., ECG abnormalities) should be reported as an AE if any of the following are applicable:

- If an intervention is required as a result of the abnormality;
- If action taken with the study drug is required as a result of the abnormality; or
- Based on the clinical judgment of the Investigator.

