9.2.2 Analysis of Safety

AEs will be classified according to the Medical Dictionary for Regulatory Activities (MedDRA) and will be presented by counting the number of subjects reporting each event by treatment. The number (percentage) of subjects reporting TEAEs and SAEs for each preferred term will be tabulated by system organ class (SOC), by SOC and severity, and by SOC and relationship to the study drug. If more than 1 event occurs with the same preferred term for the same subject, the subject will be counted only once for that preferred term using the most severe or related occurrence for the summary by severity or relationship to study drug, respectively.

If specific AEs occur in a sufficient number of subjects, an exposure-response model may be developed as a secondary analysis.

Clinical laboratory values (excluding efficacy laboratory parameters) will be summarized by treatment arm, including changes from baseline at each visit.

Vital signs and change from baseline in vital signs will be summarized descriptively at each visit by treatment arm.

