##### 3.1.3 *Definition of Baseline*

Baseline is defined as the last measurement prior to the first dose of study drug.

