### *3.6.3 Vital Signs*

Vital signs will be measured as specified in the Schedule of Procedures (Appendix A). Vital signs will be collected BID, both times prior to dosing with study drug. On Day 1, vital signs will also be collected at 2, 4, 6, and 8 hours post the morning dose. The BID measurements prior to dosing will be averaged prior to summarization.

Vital signs parameters (heart rate, blood pressure, respiratory rate, temperature, and oxygen saturation) will be listed and summarized using descriptive statistics for each treatment group by visit and timepoint. Change from baseline to each scheduled post-dose time point will also be summarized.

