## **6 CHANGES FROM PROTOCOL-SPECIFIED STATISTICAL ANALYSES**

[figure not shown]
Laboratory assessments will be summarized by incidence of abnormalities instead of change from baseline values at each visit.

[figure not shown]

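### Laboratory safety is tabulated as any out-of-range value after first dose, with no reference to baseline, so pre-existing and new abnormalities are counted alike

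*SAP*

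**What the plan says.** Protocol 7.1 names laboratory tests as a component of the primary endpoint: "Safety laboratory tests (including chemistry, hematology, coagulation parameters, and urinalysis". For their analysis, protocol 9.2.2 states: "Clinical laboratory values (excluding efficacy laboratory parameters) will be summarized by treatment arm, including changes from baseline at each visit".

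SAP 6 replaces that plan: "Laboratory assessments will be summarized by incidence of abnormalities instead of change from baseline values at each visit". It gives no reason.

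SAP 3.6.2 then sets out three outputs:

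- a count of subjects with abnormalities: "The incidence of abnormalities (as defined by normal ranges) after the first dose of study drug will be summarized";
- a count of subjects with clinically significant results after baseline;
- a listing of abnormal values.

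It does not say whether the first count is made per visit or over all visits.

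SAP 3.1.3 does define a baseline: "Baseline is defined as the last measurement prior to the first dose of study drug". For vital signs, SAP 3.6.3 uses it: "Change from baseline to each scheduled post-dose time point will also be summarized". SAP 3.6.5 says the same for ECGs.

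**The concern.** A safety table by arm should let the reader see what changed after treatment began. This one cannot. It has no denominator of subjects normal at baseline, no shift table, no rule for worsening and no grading. The second count has the same gap, because there the word post-baseline fixes a time window and makes no comparison with the earlier value. Laboratory tests are the only numeric safety component that loses its baseline reference.

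Two errors can follow. If many subjects are abnormal at entry, a real difference in new abnormalities is diluted. If the arms differ at entry by chance, the table shows a difference that the drug did not cause. Subjects enter with an acute illness, and there are about 20 on ADX-629 and 10 on placebo, so both are realistic. Safety is this trial's primary purpose, and the table feeds directly into that assessment.

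**Working it through.** The plan states no figure to reproduce. The check is of the counting rule itself.

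**Inputs from the documents.** About 30 subjects randomized 2:1 (SAP 2.2.4), so 20 on ADX-629 and 10 on placebo.

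**Inputs assumed, because the documents give none.** For one analyte: *b*, the share abnormal at baseline (10%, 30%, 50%); *r*, the share of those who are still abnormal after first dose (100%, with 70% as a check); *p*, the rate of new abnormality among subjects normal at baseline.

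**What the SAP table shows.** Displayed incidence = *b·r* + (1 − *b*)·*p*. A treatment-emergent count among subjects normal at baseline shows *p*.

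**Dilution.** Take *p* = 20% on drug and 10% on placebo, with *r* = 1.

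| *b* | ADX-629 | Placebo | Displayed difference |
|---|---|---|---|
| 10% | 0.10 + 0.90 × 0.20 = 28% | 0.10 + 0.90 × 0.10 = 19% | 9 points |
| 30% | 0.30 + 0.70 × 0.20 = 44% | 0.30 + 0.70 × 0.10 = 37% | 7 points |
| 50% | 0.50 + 0.50 × 0.20 = 60% | 0.50 + 0.50 × 0.10 = 55% | 5 points |

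When *b* and *r* are equal in the two arms, the term *b·r* cancels and the difference is (1 − *b*) × 10 points, whatever *r* is. Check at *r* = 0.7 and *b* = 30%: 0.21 + 0.14 = 35% against 0.21 + 0.07 = 28%, again 7 points.

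**Chance imbalance at baseline.** Fix the number abnormal among the 30 and let randomization send 20 to drug. The number abnormal on drug is then hypergeometric. The probability that the two baseline proportions differ by at least 30 points, in either direction, is:

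- 3 of 30 abnormal: 0.030
- 9 of 30 abnormal: 0.204
- 15 of 30 abnormal: 0.245

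**What an imbalance does to the table.** Take 9 abnormal, split 8/20 on drug and 1/10 on placebo, with no drug effect and *p* = 10% in both arms.

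- *r* = 1: 0.40 + 0.60 × 0.10 = 46% against 0.10 + 0.90 × 0.10 = 19%.
- *r* = 0.7: 0.28 + 0.06 = 34% against 0.07 + 0.09 = 16%.

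A treatment-emergent count for the same subjects has expectation 10% in both arms, with denominators of 12 and 9.

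**The case against.** The strongest reply is that a baseline-aware summary by arm already exists through adverse events. Under protocol 8.1, clinically significant abnormal findings that are detected during the trial or that "are present at Screening and significantly worsen during the clinical trial should be reported as AEs". An abnormality that needs an intervention or leads to action on study drug is also an AE. SAP 3.6.1 tabulates treatment-emergent AEs by system organ class and preferred term. This is real mitigation. It does not close the gap, because the same protocol section tells sites not to report abnormal results judged not clinically significant. A pattern of modest shifts by arm would appear in no baseline-referenced table.

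Other points narrow the concern without removing it:

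- With about 30 subjects, the listing helps to trace individuals. But only abnormal values are listed, so a normal baseline need not appear and may look the same as a missing one. A listing is also not a summary by arm.
- The change is declared, and with local laboratories a range-based summary is defensible. That supports using ranges; it does not support ignoring the baseline category.
- The word incidence, or the separate programming specifications, could be taken to mean new cases. The SAP text does not require that reading.
- The size rests on assumptions. Several exclusion criteria are redacted. If any sets laboratory limits, a high baseline abnormality rate may be impossible for that analyte.
- The trial is exploratory. One placebo subject is 10 percentage points, so the dilution alone amounts to less than one placebo subject.
- The 20% figure covers both directions. The exact split of 8/20 against 1/10 has probability about 9%, and an excess of 30 points or more on the drug side about 10%. These are figures for one analyte, however, and Appendix B lists 22 chemistry tests.

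**Conclusion.** The concern holds. As written, the laboratory summary cannot separate abnormalities present before dosing from those that arise afterwards, in a component of the primary endpoint. That conclusion follows from the text and needs no assumed rate.

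The size does depend on assumptions. Dilution is by the factor (1 − *b*) when persistence is equal in the arms: slight at 10% abnormal at baseline, a halving at 50%. Chance imbalance is the larger hazard at this sample size. With 9 or 15 of 30 abnormal at entry, a 30-point baseline gap arises for a given analyte in about 20% or 25% of randomizations, and in the worked example it produces 46% against 19% with no drug effect. The AE tables and the listing reduce the consequence, so this is a change that should be made and not a flaw that invalidates the safety analysis.

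**What to change.** Amend SAP 3.6.2 as follows.

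1. Define a treatment-emergent abnormality against the SAP 3.1.3 baseline: a value outside the local range after first dose in a subject who was not abnormal in that direction at baseline. Use those subjects as the denominator.
2. Add a shift table by arm for all subjects: baseline category (low, normal, high by local range) against worst category after first dose.
3. State that incidence is taken over all visits after first dose.
4. Optionally, show the table by inpatient status.

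The cost is SAP wording and one more table shell. No new data are needed: laboratory tests are already scheduled before dosing, and the local ranges are already needed for the planned count.

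There are two drawbacks. The treatment-emergent denominators shrink, to an expected 20(1 − *b*) and 10(1 − *b*): 18 and 9 at 10% abnormal at baseline, 14 and 7 at 30%, 10 and 5 at 50%. Three categories also do not show worsening within an already abnormal category, so those values remain visible only in the listing.

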6.3 Treatment Period – Days 1 Through 28/EOT

During the Treatment Period, all subjects will receive study drug (either ADX-629 or placebo) BID on Days 1 to 28/EOT. Treatment may commence whether a subject is hospitalized or is treated as an outpatient at Screening. The study drug will continue to be taken on an outpatient basis if a subject is discharged from the hospital prior to Day 28 for hospitalized subjects. The study drugs will each be administered orally BID, at the discretion of the Investigator, without food, defined as no food for at least 2 hours prior to dosing and at least 1 hour after dosing. Inpatient subjects will receive the study drug in the hospital. Outpatient subjects will take the study drug at home according to their usual schedule, including on Days 1, 7, 13, 22, and 28.

All subjects will also have an assessment using the NIAID ordinal scale score (see Appendix C) daily on Days 1 to 28/EOT. The NIAID score will be evaluated directly for inpatient subjects and assessed via a subject diary for outpatient subjects through Day 28. For outpatient subjects, the subject will receive instructions for subject diary completion on Day 1, while inpatient subjects will receive instructions on the day of discharge. Site personnel will monitor subject compliance between onsite study visits and contact subjects who are not compliant with diary completion. Subject compliance (for outpatient subjects only) for the subject diaries should be reviewed at the onsite visits at Days 7, 13, 22, and 28.

Inpatient subjects will have an assessment of standard of care (see Section 5.6.3) daily on Days 1 to 28/EOT (or until discharge). Outpatient subjects will have an assessment of standard of care (see Section 5.6.3) at each visit through Day 28.

In addition to study drug administration and NIAID score assessment, the procedures listed below will be performed on Days 1, 4, 7, 10, 13, 16, 19, 22, 25, and 28/EOT (inpatients). Subjects who commence treatment as outpatients or who are discharged from the hospital prior to Day 28 will undergo a telephone visit on Day 4 to assess safety and weekly onsite visits through Day 28 (on Days 7, 13, 22, and 28), which will include vital sign assessments, physical examinations, and local laboratory evaluations, as indicated below.

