6.3.4 Day 10 of Clinical Trial

The following procedures will be performed at Day 10 for subjects who are currently admitted to the hospital as inpatients:

- Perform targeted physical examination;
- Measure vital signs;
- Perform clinical laboratory assessments;
- Record concomitant medications;
- Assess NIAID score;
- Record standard of care received;
- Record AEs; and
- Administer study drug.

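### SAP 3.6.2 counts subjects with any abnormal laboratory value regardless of how often they were tested, so the laboratory component of the primary safety endpoint partly reflects time in hospital

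*SAP*

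**What the plan says.** SAP 3.6.2 gives the laboratory rule: "The incidence of abnormalities (as defined by normal ranges) after the first dose of study drug will be summarized with counts and percentages of subjects". The two arms are shown separately. It treats post-baseline clinically significant results in the same way and lists only the abnormal data. It mentions no visit, number of tests or hospital status.

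Protocol 9.2.2 had planned that laboratory values "will be summarized by treatment arm, including changes from baseline at each visit". SAP 6 withdraws this: "Laboratory assessments will be summarized by incidence of abnormalities instead of change from baseline values at each visit". Vital signs and ECGs keep by-visit summaries (SAP 3.6.3 and 3.6.5).

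Protocol 6.3 sets two testing schedules. Inpatients are seen on Days 4, 7, 10, 13, 16, 19, 22, 25 and 28 after Day 1, and sections 6.3.2 to 6.3.10 list laboratory assessments on each of those days. Subjects who start as outpatients, or who are discharged, have "weekly onsite visits through Day 28 (on Days 7, 13, 22, and 28), which will include vital sign assessments, physical examinations, and local laboratory evaluations". Their Day 4 contact is a telephone call, and the section 6.3.2 list for it has no laboratory tests. The other extra days are restricted as on Day 10: "The following procedures will be performed at Day 10 for subjects who are currently admitted to the hospital as inpatients". The Day 35 and Day 60 lists contain no laboratory tests.

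Laboratory tests are one of five components of the primary endpoint (Protocol 7.1).

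**The concern.** An ever-abnormal count grows with the number of looks. Here that number depends on whether the subject is in hospital, and hospital status after randomization is itself an outcome. Time to discharge and being alive out of hospital are both efficacy endpoints (Protocol 7.2). If one arm leaves hospital sooner, it is tested less often and shows fewer subjects with abnormalities, with no difference in laboratory risk. A chance imbalance in inpatients has the same effect. Both kinds of subject are enrolled, and neither Protocol 5.3 nor SAP 2.2.2 describes stratification by hospital status.

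This problem is separate from values already out of range at baseline. It would remain if every subject were normal before the first dose.

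**Working it through.** The plan states no figure to reproduce, so the check has four steps.

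**1. Scheduled laboratory days after Day 1 (Protocol 6.3 to 6.3.10).**

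| In hospital | Days tested | k |
|---|---|---|
| never | 7, 13, 22, 28 | 4 |
| through Day 7 | 4, 7, 13, 22, 28 | 5 |
| through Day 10 | 4, 7, 10, 13, 22, 28 | 6 |
| through Day 21 | 4, 7, 10, 13, 16, 19, 22, 28 | 8 |
| through Day 28 | all nine | 9 |

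Protocol 6.3.1 does not say whether the Day 1 sample is taken before or after the first dose. If after, the extremes become 10 and 5, and the gap is unchanged.

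**2. Chance that one subject is counted as abnormal on one analyte.** Assumptions: no drug effect and a constant per-test risk p. The documents give no p, so 5% and 10% are shown.

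- Independent tests: 1 − (1 − p)^k. At p = 5%: 1 − 0.95^4 = 18.5% and 1 − 0.95^9 = 37.0%. At p = 10%: 1 − 0.90^4 = 34.4% and 1 − 0.90^9 = 61.3%.
- Correlated tests (beta-binomial, intraclass correlation 0.4, also an assumption): 1 − B(a, b + k)/B(a, b), where B is the beta function, a = 1.5p and b = 1.5(1 − p). The factor 1.5 is (1 − 0.4)/0.4. At p = 5%: 11.3% for k = 4 and 15.8% for k = 9. At p = 10%: 21.7% and 29.5%.

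**3. Difference between arms.** If a share f of an arm stays in hospital throughout and the rest are never admitted, the arm's incidence is f × P(9) + (1 − f) × P(4). The spurious difference is the difference in f times P(9) − P(4). For shares of 30% against 60%:

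| Per-test risk | Independent tests | Correlation 0.4 |
|---|---|---|
| 5% | 0.30 × (37.0 − 18.5) = 5.5 points | 0.30 × (15.84 − 11.33) = 1.4 points |
| 10% | 0.30 × (61.3 − 34.4) = 8.1 points | 0.30 × (29.5 − 21.7) = 2.3 points |

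With 5% risk and independent tests, the arms would show 24.1% and 29.6%.

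**4. How easily such an imbalance arises.** About 30 subjects are randomized 2:1 (SAP 2.2.4), so about 20 and 10. Suppose 15 of the 30 are inpatients at entry (assumption). Under unstratified allocation, the number of inpatients in the arm of 10 is hypergeometric. The inpatient shares differ by 30 points or more with probability 0.245. One such split is 3 of 10 against 12 of 20, which is 30% against 60%. Step 3 also needs all of these inpatients to stay through Day 28, so its figures are an upper case for that split.

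**The case against.** **Size.** A reader might take 37% against 18.5% as the distortion between arms. It is not. It compares a subject in hospital for all 28 days with one never admitted, under independent tests. One subject is 5 points in an arm of 20 and 10 points in an arm of 10, so the arm differences in the working are around one subject or less. Repeat values of one analyte in one person are correlated, which favours the smaller figures. Full stays may also be uncommon. NIAID scores below 5 are excluded, so inpatients enter without supplemental oxygen, and the documents give no length of stay. A stay through Day 10 gives 6 tests, or 13.5% against 11.3% for an outpatient at 5% risk and correlation 0.4. All of this stands.

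**Status of the table.** A reader might infer that the primary safety result as a whole is compromised. The documents do not support that. The laboratory table is one descriptive component of five, SAP 3.6.2 specifies no test, and the trial is exploratory and unpowered.

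**The by-visit summary.** A reader might infer that the protocol's by-visit summary was free of the problem. It does not accumulate over tests. However, on Days 4, 10, 16, 19 and 25 it would compare arms among current inpatients only, a group selected after randomization. Only Days 7, 13, 22 and 28 give a clean comparison.

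**Visibility.** Baseline inpatient status is summarized (SAP 3.3.4), hospital outcomes are compared (SAP 3.4.2) and hospitalization data are listed (SAP 3.6.1). An imbalance could therefore be noticed, but the laboratory table would not account for it. Because only abnormal values are listed, a reader could not recover how often each subject was tested.

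**Actual testing.** Under Protocol 8.7, routine tests can stand in for trial tests, so actual counts may depart from 9 and 4. This affects the size of the effect and does not correct it.

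**Conclusion.** The point holds in a limited form. The SAP's subject-level laboratory incidence depends on the number of tests. That number runs from 4 to 9 scheduled days according to time in hospital, and nothing else in the documents corrects for it. The two arms are biased only if hospital time differs between them; if it is equal, both are raised alike. The documents cannot show whether it will differ, so a claim that the table favours ADX-629 or placebo would go beyond them.

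For full-stay inpatient shares of 30% against 60%, the spurious difference for one analyte is about 1.4 to 2.3 points with correlation 0.4 and 5.5 to 8.1 points with independent tests. These sizes rest on an assumed per-test risk of 5% to 10%, the assumed correlation and no drug effect. The direction does not depend on the particular values: the arm with more hospital time has more chances to be counted as abnormal. This is a worthwhile low-cost improvement to one descriptive table and does not invalidate the safety analysis.

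**What to change.** In SAP 3.6.2:

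- Keep the all-values incidence table, for abnormal and for clinically significant results, so that no safety finding leaves the main output. Clinically significant findings are reportable as AEs whatever the visit (Protocol 8.1), so this also keeps the laboratory and AE outputs consistent.
- Show the number of tests per subject by arm beside it.
- Add an incidence table by arm, for both kinds of result, restricted to the days scheduled for all subjects: 7, 13, 22 and 28. Use this table for the between-arm comparison. At equal per-test risk and with all four tests done, it gives inpatients and outpatients the same expected incidence (18.5% each at 5% risk, independent tests).
- Show incidence at each of those four visits with the number tested as denominator.
- Report Days 4, 10, 16, 19 and 25 separately, labelled as inpatient-only and not as a randomized comparison.

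The cost is SAP wording and one or two extra tables, with no new data. The downside is that the common-visit table alone omits abnormalities seen only on inpatient days, including Day 4, the earliest scheduled laboratory day after Day 1. That is why the all-values table should stay.
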